3.0 BACKGROUND AND RATIONALE

3.1 Introduction

Multiple Myeloma and daratumumab

Multiple myeloma is characterized by clonal proliferation of malignant plasma cells in the bone marrow, affecting an estimated 22,000 people in the US annually¹; about 75,000 people are living with, or in remission from, multiple myeloma. Disease hallmarks include presence of monoclonal protein in serum or urine and features of end organ damage, including hypercalcemia, renal insufficiency, anemia, and bone lytic lesions². Multiple myeloma remains incurable with an estimated median survival of 3-4 years with conventional therapies and longer with newer agents^{3,4}.

CD38 is a 45-kD, type II transmembrane glycoprotein that associates with cell-surface receptors in lipid rafts, regulates cytoplasmic Ca²⁺ flux, and mediates signal transduction in lymphoid and myeloid cells^{5,6}. CD38 is highly and uniformly expressed on myeloma cells^{7,8} and is expressed at relatively low levels on normal lymphoid and myeloid cells and in some tissues of nonhematopoietic origin, which makes it a potential target in the treatment of myeloma⁶. Daratumumab (HuMax-CD38, Genmab), a human IgG1k monoclonal antibody, binds to a unique CD38 epitope⁹. Preclinical studies showed that daratumumab induced target-cell killing of CD38-expressing tumor cells by means of multiple mechanisms, including complement-mediated and antibody-dependent cell-mediated cytotoxic effects, antibody-dependent cellular phagocytosis, apoptosis^{9,10}, and to a lesser extent, inhibition of the enzymatic activity of CD38.

Early phase clinical trials have established the single agent activity and efficacy of this drug in patients with relapsed and/or refractory myeloma patients¹¹. Furthermore, the drug is fairly well tolerated with infusion related reactions being the most common adverse events¹¹. Daratumumab was approved by the FDA as monotherapy for patients with relapsed/refractory multiple myeloma in November 2015. This approval was based on a single arm phase trial with 106 patients that demonstrated an objective response rate of 29% with median duration of response of 7.4 months.

Daratumumab in Combination with Lenalidomide and Dexamethasone

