4.3 Intervention

- Cycles 1 and 2: Daratumumab 16mg/kg weekly per cycle (28 days) as intravenous infusion (total duration: 8 weeks)
- Cycles 3-6: Daratumumab 16mg/kg once every 2 weeks per cycle (28 days) as intravenous infusion (total duration: 16 weeks)
- Lenalidomide maintenance therapy to be administered as standard treatment to all patients. This is administered as 5-15 mg daily 21-28/28day cycle.
- Premedications:
 - Dexamethasone 20mg/dose IV on Days 1, 8, 15, 22 for Cycles 1 and 2 and Day 1 and Day 15 for Cycles 3-6.
 - Montelukast 10mg PO for the first 4 weeks
 - Tylenol 650 mg PO prior to each dose of daratumumab
 - Benadryl 25 mg PO prior to each dose of daratumumab

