5.1 THERAPEUTIC/DIAGNOSTIC AGENTS

5.2 Daratumumab

DARZALEX™ (daratumumab) is a human immunoglobulin G1 kappa (IgG1κ) monoclonal antibody (mAb) that binds with high affinity to a unique epitope on CD38, a transmembrane glycoprotein. It is a targeted immunotherapy directed towards tumor cells that express high levels of CD38, in a variety of hematological malignancies including MM, leukemia, and non-Hodgkin's lymphoma (NHL).

Daratumumab induces lysis of CD38-expressing tumor cells, by a wide spectrum of mechanisms including complement-dependent cytotoxicity (CDC), antibody-dependent cell-mediated cytotoxicity (ADCC), and antibody-dependent cellular phagocytosis (ADCP), through activation of complement proteins, natural killer (NK) cells, and macrophages, respectively^{9,10}. For the most comprehensive nonclinical and clinical information as well as Reference Safety Information regarding daratumumab, refer to the latest version of the Investigator's Brochure [Daratumumab IB].

Preliminary pharmacodynamic studies suggest that daratumumab utilizes multiple effector cell functions, resulting in immune mediated killing of CD38-expressing tumor cells. In ex vivo experiments utilizing human bone marrow stromal cells co-cultured with primary CD38-expressing MM cells, complement-dependent cytotoxicity(CDC) occurs rapidly and demonstrates maximal myeloma cell killing by daratumumab within 1 hour of antibody- mediated activation of the complement proteins⁹ . Daratumumab-induced antibody- dependent cell-mediated cytotoxicity (ADCC) is slower in its action, with maximal ADCC by daratumumab observed at 4 hours in vitro (de Weers 2011)² . Daratumumab has also been

shown to induce antibody-dependent cellular phagocytosis (ADCP) in the presence of macrophages within 4 hours in vitro (Overdijk 2013)¹⁰. Further, in vitro studies indicated that daratumumab inhibited the cyclase activity of CD38 and stimulated the CD38 hydrolase activity (Study No. GMB 3003-013). Daratumumab induces the elimination of CD38+ populations of Tregs, Bregs and MDSCs and is hypothesized to support the clonal expansion of effector T cells.

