8.1 PRETREATMENT EVALUATION

- A complete history and physical examination with documentation of measurable disease and assessment of performance status using the ECOG scale must be performed within 4 weeks prior to study entry

The following laboratory tests will be completed within 4 weeks prior to study entry

- CBC with differential and reticulocyte count
- Chem 14, Magnesium, and Phosphate and eGFR determination
- Uric acid, LDH, and Beta-2 Microglobulin
- PT, PTT
- Serum protein electrophoresis (SPEP) and immunofixation to assess for presence and quantity of monoclonal protein (M-protein)
- 24 hour urine sample for protein electrophoresis (UPEP) and immunofixation to assess for monoclonal protein in the urine (Bence-Jones proteinuria) at baseline.
- Serum free light-chain studies, determined using the FreeliteTM assay system

- Quantitative immunoglobulins
- Review of bone marrow core biopsy and aspirate.
- Serum or urine pregnancy test in women of child-bearing potential.
- 12-lead EKG
- *Optional* Echocardiogram – 2D Echo or strain echo (Please refer to Section 10.0)
- Viral serologies
 - Hepatitis B surface antigen (HBsAg)
 - Hepatitis B surface antibody (Anti-HBs)
 - Hepatitis B core antibody (Anti-HBc)
 - Anti-Hepatitis C (HCV) antibody. If positive, will follow with HCV RNA PCR

HBV Serology

- All subjects will be tested locally for hepatitis B surface antigen (HBsAg), hepatitis B surface antibody (Anti-HBs), and hepatitis B core antibody (Anti-HBc) at Screening as indicated above.
- Additionally, subjects ongoing in the Treatment Phase who are within 6 months of starting study treatment when Protocol Amendment 03 is implemented will be required to have HBV serology performed locally upon signing the updated ICF.
 - HBV serology is not required at Screening or for subjects ongoing in the Treatment Phase who are within 6 months of starting study treatment if this was performed as part of standard of care within 3 months prior to first dose.

HBV DNA Tests:

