Molecular pathology: For MRD samples utilizing the NGS ClonoSEQ™ V2.0 (Adaptive Biotechnologies Seattle, WA) platform, immunoglobulin heavy and kappa chain variable, diversity, and joining gene segments from genomic DNA obtained from CD138+ bone marrow (BM) cell lysate or cell-free supernatant BM aspirate were amplified using universal primer sets as described elsewhere²¹. An MM clonotype was defined as an immunoglobulin rearrangement identified by NGS at a frequency of $\geq 5\%$.

Mass spectrometry based proteomics for minimal residual disease assessment: Serial urine and serum samples will be analyzed to detect clonotypic peptides representing patient's monoclonal immunoglobulin heavy and light chains using high resolution mass-spectrometry-based proteomics.

FISH and cytogenetics

Interphase FISH/cytogenetics will be performed on patients enrolled in this protocol.

DNA-based target mutations

Bone marrow aspirate samples will be analyzed for somatic mutations by exome-sequencing of targeted genes using MSKCC MyType assay.

Cell Sorting and Bone marrow cell lysate

Bone marrow aspirate storage samples will be sorted into CD 138 + and CD 138 – fractions and whole bone marrow cell lysate per HOTB SOP.

Research Blood/Serum and Urine

- a) One 7-8 mL serum tube will be collected on Day 1, Day 8, Day 15, and Day 22 of Cycle 1 and 2, Day 1 of every cycle during cycles 3-6, if and when **CR/sCR** is achieved, at the end of therapy, and at any time point if the patient has progression of disease. One 7-8 mL CPT tube will be collected on Day 1 of every cycle during cycles 1-6, if and when **CR/sCR** is achieved, at the end of therapy, and at any time point if the patient has progression of disease.
- b) Urine (random samples of 10 mL) will be collected into a standard urine collection cup and sent for analysis and storage at each of the above time points.
- c) Peripheral blood and/or urine samples from patients will be analyzed for potential serum or urine biomarkers as well as drug concentrations, and describe the association with clinical outcomes if the results of the study indicate a clinical or translational rationale for analyzing the samples. The samples will be transferred to the HOTB and will be analyzed there per institutional SOP.

Assessment/Evaluation Plan

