12.1 CRITERIA FOR THERAPEUTIC RESPONSE/OUTCOME ASSESSMENT

Disease Parameters

Minimal Residual Disease

For patients undergoing MRD or end of study assessment, the first pulled bone marrow sample will be sent for multi-parametric flow cytometry as a priority. Flow cytometry based assay to rule out MRD in bone marrow aspirates and for MRD negative status using an assay with a sensitivity of at least 1 in 10^{-5} cells. Patients with <CR/sCR are considered MRD positive. We will use the MSKCC flow cytometry MRD method which is based on 10-colors in a single tube.¹⁶. The test demonstrates highly similar results when compared to the current Euroflow approach. This test is validated and already in clinical use at MSK. Immunophenotyping of aberrant plasma cells by flow cytometry currently involves, but is not limited to, the use of the following reagents: CD138, CD19, CD45, CD38, and CD56. Characteristic changes in immunophenotypically abnormal plasma cells (CD38 bright and/or CD138 positive) include but are not limited to decreased or absent CD19 and CD45, decreased CD38, increased CD56, decreased CD27, decreased CD81, increased CD117.

Traditional Response Criteria from International Myeloma Working Group Criteria for Multiple Myeloma²²

Evaluation of Response Criteria

- a) Stringent Complete Response (sCR)
 - o Complete Response as defined below plus: Normal FLC ratio and absence of clonal cells in bone marrow by immunohistochemistry or immunofluorescence (presence/absence of clonal cells is based on the kappa/ lambda ratio).
- b) Complete Response (CR)

- Negative immunofixation on the serum and urine and disappearance of any soft tissue plasmacytomas and $\leq 5\%$ plasma cells in bone marrow
- c) Very Good Partial Response (VGPR)
 - Serum and urine M-protein detectable by immunofixation but not on electrophoresis or 90% or greater reduction in serum M-protein plus urine M- protein level $<100\text{mg per 24h}$. If the serum and urine M-protein are unmeasurable, a $\geq 90\%$ decrease in the difference between involved and uninvolved FLC levels is required in place of the M- protein criteria.
- d) Partial Response (PR)
 - $\geq 50\%$ reduction in M protein and reduction in 24-h urinary M-protein by $\geq 90\%$ or to $< 200\text{ mg per 24h}$. If the serum and urine M-protein are unmeasurable, a $\geq 90\%$ difference between involved and uninvolved FLC levels is required in place of the M- protein criteria
- e) Stable Disease (SD)

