 - Not meeting criteria for CR, VGPR, PR or progressive disease. All categories also require no known evidence of progressive or new bone lesions if radiographic studies were performed. Radiographic studies are not required to satisfy these response requirements.
- f) Progressive disease (PD)
 - Requires any one or more of the following:
 - Increase of $\geq 25\%$ of nadir in:
 - Serum M-component and/or (absolute increase must be $\geq 0.5\text{ g/dl}$. The serum M-component increases of $\geq 1\text{gm/dl}$ are sufficient to define relapse if starting M-component is $\geq 5\text{ gm/dl}$.
 - Urine M-component and/or (the absolute increase must be $\geq 200\text{ mg/24h}$
 - Only in patients without measurable serum and urine M-protein levels: the difference between involved and uninvolved FLC levels. The absolute increase must be $>10\text{mg/dl}$.
 - Bone marrow plasma cell percentage: the absolute % must be $\geq 10\%$
 - Definite development of new bone lesions or soft tissue plasmacytomas or definite increase in size of existing bone lesions or soft tissue plasmacytomas
 - Development of that can be attributed solely to the plasma cell proliferative disorder
- g) Relapse from CR
 - Any one or more of the following:
 - Reappearance of serum or urine M-protein by immunofixation or electrophoresis. (Appearance of monoclonal or oligoclonal bands that are different from original isotype may not be defined as "relapse from CR". Often times, such bands may indicate fluctuations in immunological parameters that are not reflective of MM disease. In these situations, immunofixation and electrophoresis will be interpreted by the clinician before being labeled as "relapse"^{23,24}.
 - Development of $\geq 5\%$ plasma cells in the bone marrow
 - Appearance of any other sign of progression (i.e., new plasmacytoma, lytic

bone lesion, hypercalcemia

Progression-Free Survival

PFS is defined as time of start of treatment to time of progression or death, whichever occurs first. Patients alive and progression-free at the end of study will be censored at that time.

Overall Survival

Overall survival is defined as the time of start of treatment to death from any cause. Patients alive at the end of study will be censored at that time.

Toxicity Criteria

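### Section 12.1 makes CR, and through it MRD status, depend on negative immunofixation, but has no rule for a band produced by the IgG1-kappa study drug; whether this reaches the primary count depends on an unresolved difference between 12.1 and 14.1.

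*Combined protocol and SAP*

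**What the plan says.** All references are to the combined protocol and SAP.

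- **CR.** Section 12.1(b) requires "Negative immunofixation on the serum and urine and disappearance of any soft tissue plasmacytomas", plus a marrow plasma-cell limit. The criterion is the immunofixation result itself, not the patient's own M-protein, and it has no exception. sCR builds on CR.
- **From CR to MRD.** The Minimal Residual Disease paragraph of 12.1 states: "Patients with <CR/sCR are considered MRD positive".
- **The drug.** Section 3.1 describes daratumumab as "a human IgG1k monoclonal antibody, binds to a unique CD38 epitope"; 5.2 agrees. Sections 4.3 and 9.1 schedule it weekly in cycles 1-2 and every two weeks in cycles 3-6.
- **The only band clause.** Section 12.1(g), Relapse from CR, says of "Appearance of monoclonal or oligoclonal bands that are different from original isotype" that these may not be called relapse, and leaves their reading to the clinician.
- **The only interference mentioned.** Section 11.1 says daratumumab affects the indirect antiglobulin test. It does not mention electrophoresis or immunofixation.
- **The primary endpoint.** The Statistics part of 1.1 and the Rationale in 14.1 describe conversion to MRD negativity assessed by multicolor flow cytometry, with no CR condition. The 14.1 failure rule mentions only a missing end-of-therapy marrow without earlier MRD negativity.
- **The marrow trigger.** The last footnote to the 10.0 table requires a marrow at serologic complete response.

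**The concern.** Immunofixation is used in this trial to find monoclonal protein in serum (8.1), and the treatment is a monoclonal IgG kappa. A patient may clear the myeloma, be flow negative, and still show a band that belongs to the drug. Under 12.1 as written, that patient is below CR and therefore MRD positive.

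The relapse clause does not close this gap, for two reasons. It governs loss of CR, not attainment of CR. It also protects only when the new band differs from the original isotype, so a patient whose myeloma is IgG kappa has no protection.

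Many patients could be exposed. Entry requires only VGPR (6.2) and allows serum M-protein up to 0.5 g/dL (6.3). Patients who enter below CR must therefore become immunofixation negative while on the antibody. Those who enter in CR may acquire a band after dosing begins.

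At stake are the classification of flow-negative patients in a 25-patient trial decided on 2 of 16 and 5 of 25 successes, and the reported CR/sCR results.

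**Working it through.** **1. Does dosing run up to the assessment?** Cycles 1-2 have 4 doses each (8) and cycles 3-6 have 2 each (8), so 16 doses. The last falls on cycle 6 day 15, two weeks before the sixth 28-day cycle ends. The drug is on board at the end-of-therapy visit.

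**2. Is a band plausible then?** The documents give no pharmacokinetics and no immunofixation limit, and do not say that the drug is visible on the assay. Assumptions: one compartment, volume 45-65 mL/kg, half-life 10-20 days, detection limit about 0.1-0.25 g/L. Each 16 mg/kg dose adds 16/V, that is 16/65 = 0.25 to 16/45 = 0.36 g/L, and decays by exp(-ln2 × t / half-life). Summing the 16 doses:

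| Time | Modelled serum drug, g/L |
|---|---|
| Trough one week after the eighth weekly dose | 0.39-1.11 |
| Two weeks after the last dose | 0.15-0.58 |
| Three weeks after the last dose (end-of-therapy visit one week late, as the window allows) | 0.09-0.46 |
| 90 days after the last dose | 0.001-0.04 |

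At end of therapy the range overlaps the assumed limit and extends above it. A band is plausible in some patients. It is not shown for all.

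**3. Which rule decides the primary endpoint?**

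| Patient at end of therapy | 12.1 governs | Flow-only wording of 1.1 and 14.1 governs |
|---|---|---|
| Flow negative, no band, other CR criteria met | success | success |
| Flow negative, drug band the only residual finding | failure | success |

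Section 14.1 neither repeats nor cancels the 12.1 sentence, so both readings are open.

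**4. Reproduce the plan's design.** Inputs from 14.1: 16 then 9 patients, continue if at least 2 successes, promising if at least 5 of 25, rates 10% and 30%.

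P(promising | p) = Σ over x = 2 to 16 of C(16,x) p^x (1-p)^(16-x) × P(Bin(9,p) ≥ 5-x)

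This gives 0.0951 at p = 0.10 and 0.9030 at p = 0.30, within the stated 0.10 error limits. An exhaustive minimax search returns the same design. The sample size is not in dispute.

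**5. Effect if 12.1 governs.** Let m be the share of true flow conversions held below CR by a drug band, so the counted rate is true rate × (1-m). The documents do not give m.

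| m | Counted rate (true 30%) | Power | Wrong stage 1 stop | Type I error (true 10%) |
|---|---|---|---|---|
| 0% | 27/90 = 30.0% | 0.903 | 0.026 | 0.095 |
| 10% | 27.0% | 0.837 | 0.045 | 0.067 |
| 20% | 24.0% | 0.742 | 0.075 | 0.044 |
| 35% | 19.5% | 0.544 | 0.152 | 0.020 |
| 50% | 15.0% | 0.310 | 0.284 | 0.007 |

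The 35% row would apply if, by assumption, 35% of converters had IgG-kappa myeloma and every one were misclassified. If half of them were, m = 17.5%, the counted rate is 24.75% and power is 0.768. On the most literal reading any drug band fails CR, whatever the myeloma isotype, so the loss need not be confined to IgG-kappa patients.

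**The case against.** The strongest reply is that 1.1 and 14.1 define the endpoint by flow cytometry and the decision rules name no CR condition. If those sections govern, the whole power loss in step 5 disappears. This stands, and it limits the point: a reader might infer that the 2/16 and 5/25 decisions will certainly count true conversions as failures, but the documents support that only if 12.1 governs.

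Second, every quantity behind the size is assumed: volume, half-life, assay limit, isotype share and misclassified fraction. This also stands. The table is a range, and 0.54 is not an estimate for this trial.

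Third, a delayed marrow trigger costs little. Section 10.0 keeps the end-of-therapy marrow mandatory unless MRD negativity was confirmed earlier, so the primary assessment still takes place.

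Fourth, a reader might infer that a drug band would falsely end the duration of MRD negativity. The documents and the model largely contradict this. Under 12.1 a converter is already immunofixation negative while on the drug, and drug levels only fall after the last dose. A new drug band is then close to excluded, except after conversion in the first weeks, while troughs are still rising. Section 14.1 does not list relapse from CR as a duration event, and the sustained endpoint is read one year after treatment, when the modelled drug is gone.

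What survives is the missing rule for attaining CR, the lack of protection for IgG-kappa patients in the relapse clause, and two open readings of the primary endpoint.

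**Conclusion.** The concern holds in a conditional form. Following 12.1 literally can turn a flow-negative patient into a primary-endpoint failure because of a band from the study drug. Under the flow-only wording the primary count is unaffected, but CR/sCR classification, the serologic-CR marrow trigger and relapse from CR in IgG-kappa patients remain exposed.

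The size cannot be obtained from the documents. For assumed losses of 0-35% of true conversions, power at a 30% true rate runs from 0.90 to 0.54. The error is conservative: type I error drops below 0.095, so an active regimen could be wrongly discarded, but no false positive is created. The conclusion rests on the inference that an infused IgG-kappa antibody can show on an assay for monoclonal protein, which the documents do not state. This should be fixed before outcomes are classified; it does not invalidate the design.

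**What to change.** 1. **Reconcile 12.1 with 14.1.** State whether the primary endpoint is flow status alone or flow negativity plus CR/sCR, and word both sections the same way.
2. **Add a drug-band rule to 12.1.** For example: an immunofixation band attributed to daratumumab does not count against CR or sCR and is not relapse from CR. In a flow-negative patient whose only residual finding is an IgG-kappa band, settle its origin on serum already stored under 10.0. A daratumumab-specific immunofixation test would serve, or the planned mass spectrometry, for which "Serial urine and serum samples will be analyzed to detect clonotypic peptides representing patient's monoclonal immunoglobulin heavy and light chains". Apply the same rule to the serologic-CR marrow trigger.
3. **Protect the method comparison.** Section 14.1 compares flow with mass spectrometry by kappa. If mass spectrometry helps to settle MRD status, that comparison is no longer independent. Use raw flow status in the kappa analysis, and report how many patients were reclassified.

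The cost is about a paragraph of text, a few tests on stored serum and a short delay in classifying those patients. No new visit or sample is needed. If flow status alone is chosen in item 1, the primary endpoint needs no reflex test, and the rule in item 2 then serves only the CR/sCR classification, the relapse label and the marrow trigger.
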